One of the most frequently used alternative therapies is herbal medicine that act as anti-ROS agents preventing DNA damage has been used alongside conventional treatment regimens (Li et al, 2016). One of the agents that receives particular strong interest is coffee. Coffee is considered as a major source of dietary antioxidants; some are present in the green bean, whereas others are generated during roasting. Coffee roasting, the process of the heating of green coffee beans transforming them into black coffee beans, transforms the chemical and biological properties of coffee beans (Wei et al. 2012 and Jeong et al, 2013).

Regarding oral cancer, some studies reported an association of high coffee consumption to an augmented risk of oral cancer (Bundgaard et al, 1995 and Franco et al, 1989) while others showed a clear inverse association with the risk of oral cancer (Naganuma et al, 2008 and Hildebrand et al, 2013). Recently, there have been reports of a protective effect of coffee consumption on oral cancer from two recent meta-analysis (Zhang et al, 2015 and Li et al, 2016). To our knowledge, only two studies were done to assess the effect of coffee ingredients (cafestol and kahweol) on oral squamous cell carcinoma cell lines (Chae et al, 2014 and Kotowski et al, 2015).

Due to these controversial findings concerning the effect of roasted coffee and absence of data on unprocessed (green coffee), our study aims to investigate the effect of different coffee beverage as regard apoptosis and proliferation carried out in OSCC cell lines.

Rationale for carrying out this study:

The main objective of our study was to evaluate anti proliferative and apoptotic activity of green coffee, in comparison to roasted coffee and decaffeinated coffee on cultured OSCC cell line.

PICO

Patient / Population: Human Oral squamous cell carcinoma cell line

Intervention1: Green coffee

Intervention2: Roasted coffee

Intervention3: Decaffeinated coffee

Control: no application

Outcome:

Primary outcome 1: assessment of proliferative activity OSCC cell line treated with coffee using **ELISA**.

Primary outcome 2: Assessment of apoptotic cell death of OSCC cell line treated with coffee using **RT-PCR**.

	Outcome measure	Measuring device	Measuring unit
1- Primary1	Proliferative activity	ELISA	Comparative (light absorbed) numerical value
1- Primary2	Apoptotic cell death	RT-PCR	Comparative (fold changes) numerical value

Research question

Do different types of coffee affect proliferation and/or apoptosis of human oral squamous cell carcinoma cell line?

III. Methods

A) Samples, intervention and outcomes

1) Material:

1. Cell Lines:

Oral squamous cell carcinoma cell line (SCC15), purchased from the confirmatory diagnostic unit, R&D sector, Vacsera, Cairo, Egypt.

2. Coffee extract:

Green coffee, roasted coffee and decaffeinated coffee from local Egyptian market, Cairo, Egypt. The peels and seeds were manually separated.

2) Methods:

Intervention:

Oral squamous cell carcinoma cell line samples will be cultured with and without the addition of green coffee, roasted coffee or decaffeinated coffee extract.

Collecting Samples:

Oral squamous cell carcinoma cell lines will be purchased from (veterinary serum & vaccine research institute, VACSER).

Inclusion Criteria:

Only human cell lines.

Exclusion Criteria:

Animal cell lines.

Mixed tumors.

Sample preparation:

Cells will be sub-cultured in a 96-well plate.

Monolayer cells will be incubated for 48 hours at 37°C in the 5% CO₂ incubator.

After 48 hours, cells will be fixed in wells for 1 hour in trichloro-acetic acid (50%-5 micro liter) which was added to the wells by a multichannel pipette.

Cells will be then washed with tap water and left to dry for 1 hour.

- Sulphorhodamine B stain will be added (50 μ l) and left for half an hour.
- Excess stain will be washed with 5% glacial acetic acid and then attached stain was recovered with EDTA buffer (100 μ l).

Measurements:

a) MTT assay for cellular viability:

1. One ml of cells (50,000-100,000 cells/ml) will be plated into each well of 96-well culture plate for 24 hours before the MTT assay.
2. The cells will be incubated for 24 h in CO₂ incubator.
3. After treatment of cells with antibiotics and antifungal for 24-72 h, experimental media will be removed, and cells will be washed with PBS.
4. Coffee extracts will be added for cell lines with serial dilutions (100 μ g/ml, 10 μ g/ml, 1 μ g/ml, 0.1 μ g/ml, and 0.01 μ g/ml), incubated for 48 hours and then will be washed by PBS twice.
5. The cells will be incubated with medium containing 0.5 mg/ml MTT in CO₂ incubator at 37°C for 4 h.
6. The medium will be aspirated, and the formazan product will be solubilized with dimethyl sulfoxide (DMSO).
7. Absorbance at 570 nm will be measured for each well using a microplate reader (BioTek,Flx 800).

The percentages of cytotoxicity and cell viability are calculated using the following equations:

% cytotoxicity = 1 - [means absorbance of treated cells/mean absorbance of negative control], % viability = 100 - % cytotoxicity.

Measurement of proliferative activity:

Enzyme assay (ELISA) will be used to estimate the inhibitory effect green coffee, roasted coffee, decaffeinated coffee on **Epidermal growth factor Receptor (EGFR)** protein.

Sample preparation for ELISA:

Cell lysis for cell culture samples will be carried by spinning down cells for 15 minutes at 1200 RPM. Cell pellets are washed once in cold PBS. Cells are re-suspended in Lysis Buffer to a concentration of 1.5x10⁶ cells/mL, are incubated for 1 hour at room temperature with gentle shaking. Cells are centrifuged at 200 x g for 15 minutes. The supernatant will be diluted at least 50-fold in 1X Assay Buffer (5 μ L supernatant + 245 μ L 1X Assay Buffer) for the assay.

1. Prepared biotin antibody is added to samples in different wells.

2. Then prepared Streptavidin horseradish peroxidase (HRP) solution is added after washing.

3. Tetramethylbenzidine (TMB) Solution is added to each well and incubated at room temperature. Stop Solution is added to each well. Readings will be done at 450 nm immediately

Apoptosis activity assay:

Following treatment with green coffee or roasted coffee or decaffeinated coffee for 24 h, the cells are harvested, lysed and tested with RT-PCR using specific primers to estimate the fold change of the gene expression of Caspase-3, bax, bcl-xl and p53.

7. Calculated sample size

No sample size estimation could be done, as the primary outcome is not a measured outcome.

8. Description of study sample

No sample size could be applied on cell line experiments as we generate millions of naturally randomized cells.

9. Intervention for each group

Green coffee extract will be introduced to the 1st group, while roasted coffee will be added to the 2nd group. The 3rd group will be treated with decaffeinated coffee.

10. Outcomes

Apoptosis (Gene expression of Caspase – 3, EGFR).

Prioritization of Outcome	Outcome	Method of measurement	Measuring unit
Primary1	EGFR expression using ELISA	Robonek P2000 ELISA reader	IC 50 µg / ml
Primary2	Caspase-3, bax, bcl-xl and p53 gene expression using RT – PCR	Rotorgene system	Fold change FLD=e-ΔΔCT

B)Assignment to intervention

This study is non-randomized.

11. Sequence generation

Sequence generation is not applied on cell line experiments.

12. Allocation concealment

Allocation concealment is not applied on cell line experiments.

13. Implementation

Implementation is not applied on cell line experiments.

C) Blinding

14. Blinding

Blinding is not applied on cell line experiments.

D) Statistical methods

Data will be analyzed using IBM SPSS advanced statistics (Statistical Package for Social Sciences), version 21 (SPSS Inc., Chicago, IL). Numerical data will be described as mean and standard deviation or median and range. Categorical data will be described as numbers and percentages.

IV- References:

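### The control is defined as nothing applied, with no carrier-only or identically handled control, so coffee-versus-control comparisons cannot separate coffee from its carrier and handling

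*Protocol*

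**What the plan says.** The only explicit definition of the control is in the PICO list: "Control: no application". The Intervention paragraph under Methods is consistent with it: cell line samples "will be cultured with and without the addition of green coffee, roasted coffee or decaffeinated coffee extract". Section 9 (Intervention for each group) lists the three coffee groups and no control group.

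In the MTT assay, step 3 takes the medium off and rinses the cells with PBS. Step 4 then says "Coffee extracts will be added for cell lines with serial dilutions", at five concentrations from 100 down to 0.01 µg/ml. The wells are "incubated for 48 hours and then will be washed by PBS twice". The cytotoxicity equation divides by the "mean absorbance of negative control", a term defined nowhere else.

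On how the extract is made, the Material section gives the market source and adds "The peels and seeds were manually separated". It names no extraction solvent or diluent. DMSO appears only at read-out, to dissolve the formazan.

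**The concern.** An extract dosed in µg/ml over a dilution series has to be carried in some liquid. A treated well therefore gets coffee, carrier and the step of adding them. A control well, on the protocol's own definition, gets nothing. The contrast between them estimates the sum of these effects, not the effect of coffee.

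This matters because the research question asks whether the coffees affect proliferation or apoptosis, which can only be answered against a control. MTT cytotoxicity is computed directly against a control. The two primary outcomes, EGFR by ELISA and gene expression by RT-PCR, also need a reference if they are to be read as inhibition or as fold change. Untreated cells are the only candidate that the protocol describes.

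**Working it through.** The protocol states no sample size, power, effect size or standard deviation, so there is no planned figure to reproduce. The check has two parts.

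**1. What treated and control wells receive, as written**

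| Element | Treated wells | Control wells |
|---|---|---|
| Coffee | Yes, five concentrations (MTT) | No |
| Carrier liquid | Implied, not named | None described |
| Volume added | Not stated | Not stated |
| Liquid restored after step 3 | The extract preparation | Not stated |
| 48 h incubation and two PBS washes (MTT) | Yes | Not stated |
| 24 h treatment (RT-PCR) | Yes | Not stated |

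Only the first row is meant to differ. For the other rows the protocol does not say that the wells are alike, and for the carrier row the PICO definition says that nothing is applied.

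**2. How a carrier or handling effect passes through the formulas**

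Inputs: the MTT equation from the protocol; *c*, the true proportional loss of absorbance caused by coffee (assumed); *v*, the proportional loss caused by carrier and handling (assumed, because the protocol gives none). The two are taken to act independently, so they multiply.

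With an untreated control, treated absorbance over control absorbance is (1 − v)(1 − c), so

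apparent cytotoxicity = 1 − (1 − v)(1 − c).

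| Assumed v | c = 0 | c = 30% | c = 50% |
|---|---|---|---|
| 0% | 0% | 30.0% | 50.0% |
| 2% | 2% | 31.4% | 51.0% |
| 5% | 5% | 33.5% | 52.5% |
| 10% | 10% | 37.0% | 55.0% |
| 20% | 20% | 44.0% | 60.0% |

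Example: v = 10%, c = 30% gives 1 − 0.90 × 0.70 = 37.0%. With a matched carrier control the factor (1 − v) is in numerator and denominator, cancels, and the equation returns c.

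*IC50.* Assume a dose curve with Hill slope 1 and the same carrier loss v at every concentration. Let x be concentration divided by the true IC50. The apparent IC50 solves (1 − v)/(1 + x) = 0.5, so x = 2(1 − v) − 1. For v = 5, 10 and 20% the apparent IC50 is 0.9, 0.8 and 0.6 times the true one. If the carrier instead falls in proportion to the tenfold dilutions, a 5 to 10% loss at 100 µg/ml is 0.5 to 1% at 10 µg/ml. The distortion then sits almost wholly at the top concentration.

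*RT-PCR.* If untreated cells are the calibrator, apparent fold = carrier fold × coffee fold. A true fold of 2.0 with an assumed carrier fold of 1.1, 1.25 or 1.5 reads as 2.2, 2.5 or 3.0.

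*Coffee against coffee.* With a shared carrier and handling, the ratio of two viabilities is (1 − v)(1 − 0.5)/[(1 − v)(1 − 0.3)] = 0.714 for every v. A common carrier cannot create a difference between coffees. A difference in percentage points does shrink by the factor (1 − v): from 20 to 55.0 − 37.0 = 18 points at v = 10%.

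**The case against.** The strongest reply is that a short PICO entry is being read too literally. Next to the Intervention sentence it may mean only that no coffee is given. It does not say that control wells miss the medium change, incubation or washes. If the extract is taken up in plain culture medium and all wells are handled alike, the bias is zero. The stated main objective compares green coffee with roasted and decaffeinated coffee, where a common carrier does no harm. All this stands, and it limits the point to a possible bias in the contrasts with control.

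It does not remove the point. The protocol states a rule for the control, names no carrier, and nowhere says that handling is matched. A shared carrier across the three coffees is not stated either.

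A reader might infer more than the text supports:

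- **That adding extract dilutes the medium in treated wells, by more at higher concentrations.** MTT step 3 removes the medium before step 4 adds the extract, and the protocol lists concentrations, not volumes. Equal volumes per well are compatible with the text.
- **That the MTT equation and the fold change certainly use the untreated cells as denominator.** The equation's negative control is not tied to the PICO entry, and no calibrator is named for RT-PCR. A carrier-treated well would also fit the term.
- **That both primary outcomes are biased by a known amount.** The cytotoxicity percentages above are assumed and concern MTT, which is not a primary outcome.

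**Conclusion.** The concern holds as a weakness of a stated design rule, not as a demonstrated bias. As written, coffee versus control does not isolate coffee, because the control is defined as nothing applied and no passage supplies a carrier-only or identically handled well. MTT cytotoxicity is exposed if its undefined negative control is the PICO control. The ELISA and RT-PCR results are exposed if untreated cells are their reference.

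The size, and even the direction, cannot be derived from the protocol. The illustrative figures rest on an assumed v of 0 to 20%, carrier folds of 1.1 to 1.5, independent effects of coffee and carrier and, for the IC50, a Hill slope of 1. Comparisons between coffees are protected from a spurious difference only if all three share carrier, volume and handling, which the protocol should state.

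**What to change.** 1. Name the liquid in which each coffee extract is prepared and diluted.
2. In PICO and in the Intervention paragraph, replace "Control: no application" with the same volume of that carrier without coffee. Require the same medium change, incubation time and washes as the treated wells of the same assay. The duration must follow each assay (48 h for MTT, 24 h for RT-PCR), so the MTT steps should not be carried over to the others.
3. Keep the carrier fraction constant across the five MTT dilutions, so that only the coffee concentration varies.
4. State that this control is the negative control in the cytotoxicity equation, the reference for EGFR by ELISA and the calibrator for the RT-PCR fold change. List it in section 9.
5. State whether the three coffees share one carrier. If they do not, provide one matched control per carrier.

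The cost is small. The existing control wells receive carrier instead of nothing, and no assay is added. Extra wells are needed only if the coffees use different carriers. The work lies in settling the carrier and the dilution scheme before the experiment starts.

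### Primary outcome 2 is labelled apoptotic cell death but measured only as transcript fold changes, and the lead line of section 10 contradicts its own table on which genes count

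*Protocol*

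**What the plan says.** The protocol describes Primary outcome 2 in four places.

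- **PICO, Outcome.** The outcome is "Assessment of apoptotic cell death of OSCC cell line treated with coffee using" RT-PCR. The small table beneath repeats apoptotic cell death as the outcome, with RT-PCR as the device and fold change as the unit.
- **Apoptosis activity assay (Measurements).** After 24 h of treatment the cells are harvested, lysed and tested by RT-PCR "to estimate the fold change of the gene expression of Caspase-3, bax, bcl-xl and p53".
- **Section 10, lead line.** "Apoptosis (Gene expression of Caspase – 3, EGFR".
- **Section 10, table, Primary 2.** "Caspase-3, bax, bcl-xl and p53 gene expression using RT – PCR", reported as fold change.

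EGFR has a different role elsewhere. The section on measuring proliferative activity uses it as the target protein, and the section 10 table gives Primary 1 as "EGFR expression using ELISA". No RT-PCR for EGFR is described.

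The research question asks "Do different types of coffee affect proliferation and/or apoptosis of human oral squamous cell carcinoma cell line". It sets no direction, and the protocol does not say how the four genes should move or how they combine.

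**The concern.** There are two separate faults in how a primary outcome is fixed.

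First, the label claims more than the assay measures. RT-PCR on lysed cells gives relative transcript abundance. It does not say how many cells entered apoptosis or died. A study run as written would report apoptotic cell death on the strength of gene expression alone.

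Second, the lead line of section 10 and the table directly under it cannot both be right about which markers define apoptosis. A marker of one primary outcome (proliferation) is filed under the other (apoptosis), and three of the genes to be assayed are missing.

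At stake is the headline statement on apoptosis. With no expected direction and no rule for reading the four genes together, a mixed result has no agreed interpretation. By general background, not stated in the protocol, bcl-xl works against apoptosis and caspase-3 works for it. If both rose, nothing in the text would prevent the result from being reported as apoptosis.

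**Working it through.** **Step 1: set the definitions side by side.**

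| Place | Construct named | Markers | Assay and unit |
|---|---|---|---|
| PICO text and table | apoptotic cell death | none named | RT-PCR, fold change |
| Apoptosis activity assay | apoptosis | caspase-3, bax, bcl-xl, p53 | RT-PCR, fold change |
| Section 10, lead line | apoptosis | caspase-3, EGFR | gene expression, assay not named |
| Section 10, table | gene expression | caspase-3, bax, bcl-xl, p53 | RT-PCR, fold change |

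The PICO entry, the assay paragraph and the section 10 table agree on assay and unit. The last two also agree on the genes. The lead line is the one outlier: it shares only caspase-3 with the table, omits bax, bcl-xl and p53, and adds EGFR.

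**Step 2: does any other measurement cover cell death?** The only cell-level measure is the MTT assay. It gives viability and percentage cytotoxicity from absorbance relative to a negative control. Loss of viability is not specific to apoptosis, and MTT appears in neither outcome table. It is also read after 48 h of exposure, against 24 h for RT-PCR. It therefore does not supply the missing measurement.

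**Step 3: how many ways can Primary 2 be read?** The protocol states no alpha, test, power or sample size, so it has no figure of its own to reproduce. The following is illustration under stated assumptions.

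Inputs: 4 genes (section 10 table); 3 coffees (section 9); 1 untreated control (PICO). Assumed: two-sided alpha of 0.05 per test.

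- Coffee-versus-control comparisons: 4 × 3 = 12.
- If the tests were independent: 1 − 0.95^12 = 1 − 0.540 = 46.0%. At an assumed alpha of 0.01 it would be 1 − 0.99^12 = 11.4%.
- Independence does not hold, because the three coffees share one control. With equal group sizes and a common variance, two such contrasts correlate at (σ²/n) / (2σ²/n) = 0.5.
- Simulation of 400,000 multivariate normal draws, correlation 0.5 between coffees, between-gene correlation r assumed:

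| r between genes | Chance of at least one false positive in 12 |
|---|---|
| 0 | 41.5% |
| 0.3 | 39.2% |
| 0.5 | 35.5% |
| 0.8 | 26.9% |

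- For comparison, one pre-named gene against control for three coffees gives 1 − 0.95^3 = 14.3% under independence. Allowing for the shared control, the r = 0 row implies 1 − (1 − 0.4147)^(1/4) = 12.5%.

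The result in Steps 1 and 2 does not depend on any of these figures.

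**The case against.** The strongest reply is that the protocol is less inconsistent than it looks. The PICO entry names the construct and puts RT-PCR and fold change beside it, so what is measured is disclosed. The assay paragraph and the section 10 table then give the operational detail, with the same four genes each time. On that view there is one outcome with a loose headline, plus one careless lead line that may have been meant as a summary of both primaries. This largely stands as a description of how the text arose. It does not remove the faults: the headline still names something the assay does not measure, and the lead line still contradicts its table.

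A reader might infer more, and the document does not support it in three respects.

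- **Three rival primary variables, open to choice after the fact.** The PICO entry and the table share assay and unit, so they are construct and detail, not competing variables. Only the lead line is at odds.
- **Any one of 12 comparisons, in either direction, is allowed to count as a positive result, with a 46% error rate.** The protocol is silent on tests, alpha and success criteria, and silence is not permission. Multiplicity handling is commonly left to the statistical analysis plan, which is not at hand. The 46% also needs independence, which a shared control rules out. Extending the count to coffee-versus-coffee contrasts under independence is less tenable still, because the six pairwise contrasts among four groups are linearly dependent. No figure is offered for that.
- **The results would say nothing about apoptosis.** Fold changes in these genes are indirect evidence on apoptosis-related expression. What they cannot carry alone is a claim of apoptotic cell death.

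One might also want caspase-3 made the sole primary gene, as the only one in both section 10 texts. Because one of those texts is defective, overlap is a weak reason, and the choice is better left to the sponsor.

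**Conclusion.** The point holds as a defect in how the protocol fixes a primary outcome. Primary 2 carries a label (apoptotic cell death) that no listed outcome measures, and the section 10 lead line conflicts with its own table on three omitted genes and one misplaced marker. Both follow from the text alone and need no assumption. A later analysis plan could not settle them without choosing between conflicting protocol statements.

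The absence of an expected direction or joint reading for the four genes makes this worse, because a mixed pattern could be presented as apoptosis. The roughly 27% to 42% chance of at least one false positive over 12 comparisons only illustrates the scale. It assumes a two-sided alpha of 0.05, equal groups with a shared control, and between-gene correlation from 0.8 down to 0. It is not an error rate that the protocol commits to.

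The correction is worth making before data are seen: it bears on a headline claim and costs very little.

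**What to change.** 1. Use one definition of Primary 2 in the PICO text, both outcome tables and the section 10 lead line: expression of apoptosis-related genes (caspase-3, bax, bcl-xl, p53) by RT-PCR, as fold change.
2. Remove EGFR from the apoptosis line and keep it under Primary 1 only.
3. Limit the planned conclusion to gene expression, and do not claim apoptotic cell death from these data.
4. State, before the data are seen, the expected direction for each gene and how the four are read together, either by a lead gene or by a combining rule, at the sponsor's choice. Say what a mixed result will be taken to mean.

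These are changes of wording and prespecification, and the same assays are run. The cost is a narrower claim and, if a lead gene is chosen, supportive status for the other three.

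### The MTT equations lack a factor of 100, so viability as written is 99 + r and complete cell kill reads as 99% viable

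*Protocol*

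**What the plan says.** In the Protocol, Methods, Measurements, item a) MTT assay for cellular viability, step 4 sets out the exposure: "Coffee extracts will be added for cell lines with serial dilutions", at five ten-fold steps from 100 down to 0.01 µg/ml. The raw measurement is given in step 7: "Absorbance at 570 nm will be measured for each well using a microplate reader". The conversion to reported results is introduced by the sentence "The percentages of cytotoxicity and cell viability are calculated using the following equations". The two equations then follow on one line: "cytotoxicity = 1 - [means absorbance of treated cells/mean absorbance of negative control], % viability = 100 - % cytotoxicity". Both left-hand sides carry a percent sign. No other conversion, scaling or factor of 100 for these quantities appears in the Protocol.

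**The concern.** The two equations put the same named quantity on two different scales. In the first, the whole is 1; in the second, it is 100. An analyst who enters them as printed gets a viability between 99 and 100 for every condition in which the treated absorbance lies between zero and the control value. An extract that killed every cell would look almost inert.

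These are the only equations given for the MTT assay. They therefore govern the viability results for all three coffee extracts at all five dilutions.

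**Working it through.** **Inputs**, all from the MTT item of the Protocol:

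- r = mean absorbance of treated cells divided by mean absorbance of the negative control.
- Stated cytotoxicity: "cytotoxicity = 1 - [means absorbance of treated cells/mean absorbance of negative control", that is, c = 1 − r.
- Stated viability: "viability = 100 - % cytotoxicity", that is, v = 100 − c.
- Intended scale: percentages, from the introductory sentence and the percent signs.

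The Protocol gives no numerical viability or cytotoxicity result, so there is no figure of its own to reproduce. The check is by substitution.

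**As written:** v = 100 − (1 − r) = 99 + r.

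**As intended:** C = 100 × (1 − r), so V = 100 − C = 100r.

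**Error:** v − V = 99 + r − 100r = 99 × (1 − r) percentage points.

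The r values below are illustrative; the Protocol supplies none.

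| r | Stated cytotoxicity | Intended cytotoxicity (%) | Stated viability (%) | Intended viability (%) | Viability error (points) |
|---|---|---|---|---|---|
| 1 | 0 | 0 | 100 | 100 | 0 |
| 0.90 | 0.10 | 10 | 99.90 | 90 | 9.9 |
| 0.75 | 0.25 | 25 | 99.75 | 75 | 24.75 |
| 0.50 | 0.50 | 50 | 99.50 | 50 | 49.5 |
| 0.25 | 0.75 | 75 | 99.25 | 25 | 74.25 |
| 0.10 | 0.90 | 90 | 99.10 | 10 | 89.1 |
| 0 | 1 | 100 | 99.00 | 0 | 99 |

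**Contrast between two conditions:** for r = 0.80 and r = 0.40, the stated difference is 99.80 − 99.40 = 0.4 points. The intended difference is 80 − 40 = 40 points, which is 100 times larger.

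**Half-effect point:** a stated viability of 50 would need 99 + r = 50, so r = −49, which is impossible for an absorbance ratio. The half-effect dose can still be found from the raw ratio at r = 0.5, but not as a 50% point on the viability scale the Protocol defines.

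**The case against.** The best defence is that this is loose notation. Writing a percentage as one minus a ratio, with 0.5 understood as 50%, is common, and spreadsheet percent formatting does the same. On that reading the 1 means 100%, the equations agree, and the intended quantity is clear. Literal use would also expose itself at once, because every result would fall between 99 and 100.

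A second line of defence is that little depends on it. The outcome tables (PICO, and section 10, Outcomes) list proliferative activity (EGFR by ELISA) and apoptosis gene expression (RT-PCR) as primary, not MTT viability. The IC50 unit in section 10 is attached to the EGFR measurement and is not linked to MTT. No sample size or decision rule uses these percentages. The printed rule is a linear rescaling, v = 99 + V/100, so rank order and any test unaffected by linear rescaling are unchanged, and the correct values can be recovered.

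The second argument stands in full and is why the point is minor. The first does not remove the error. The same line writes the whole as 1 in one equation and as 100 in the next, for two quantities that both carry a percent sign, so the reader has to depart from the printed formula to make it work. The line was read from PDF, but its brackets balance and it shows no gap or redaction, so nothing suggests that a factor was lost in extraction.

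**Conclusion.** The equations are wrong as written. Followed literally, they give a viability of 99 + r instead of 100r, an error of 99 × (1 − r) percentage points. That is zero when the extract has no effect and 99 points at complete kill. Cytotoxicity is understated by a factor of 100 wherever r differs from 1.

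The algebra rests on no assumption beyond reading the line as printed. Harm arises only if an analyst applies it literally. Severity is minor: raw absorbances are unaffected, the intended rule is easy to infer, and the Protocol ties neither primary outcome to the MTT percentages.

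**What to change.** Replace the first equation and keep the second:

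- % cytotoxicity = 100 × (1 − mean absorbance of treated cells / mean absorbance of negative control)
- % viability = 100 − % cytotoxicity

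Viability then equals 100r: 0% at complete kill, 50% at r = 0.5 and 100% at no effect. The cost is one formula line, with no new wells or data. If any percentages have already been computed with the printed rule, recalculate them from the raw absorbances.

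### The MTT equation has no blank term and no cell-free wells are planned, so background absorbance understates cytotoxicity; an added coffee-specific error is possible but probably small

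*Protocol*

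**What the plan says.** In the Protocol, Measurements, part a) (MTT assay), step 7 states: "Absorbance at 570 nm will be measured for each well using a microplate reader". The equations after that step use the readings directly, through the ratio "means absorbance of treated cells/mean absorbance of negative control". In full they read: "cytotoxicity = 1 - [means absorbance of treated cells/mean absorbance of negative control], % viability = 100 - % cytotoxicity". The only comparator named, in the PICO list, is "Control: no application", that is, untreated cells. No blank, cell-free well, extract-only well, background subtraction or reference wavelength appears anywhere in the protocol.

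Three other statements bear on the point:

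- After exposure to the extracts the cells are "incubated for 48 hours and then will be washed by PBS twice" (step 4). Medium containing MTT is then added (step 5) and aspirated before the formazan is dissolved in DMSO (step 6).
- The introduction says of coffee: "Coffee is considered as a major source of dietary antioxidants; some are present in the green bean, whereas others are generated during roasting". It describes roasting as "the process of the heating of green coffee beans transforming them into black coffee beans, transforms the chemical and biological properties of coffee beans".
- The two primary outcomes are EGFR by ELISA and gene expression by RT-PCR (PICO and section 10, Outcomes). MTT viability is neither of them.

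**The concern.** An MTT reading is an optical signal. Plate plastic, DMSO and leftover reagent may absorb some light with no living cell present. If that background is not subtracted, it counts as surviving cells in every well, and the stated ratio moves toward 1.

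A second contribution could arise in treated wells only. Extract that is coloured, or that reduces MTT chemically, would add signal if any remained at the reading. The protocol itself says that green and roasted beans differ in colour and antioxidants, so the amount need not be the same for each coffee. Comparing the coffees is the study's stated objective.

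The timing matters too. Blank wells are a plate-layout decision: if they are not plated, no later analysis can supply the correction.

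**Working it through.** **Inputs.** The equation, the single 570 nm reading, the untreated control and the wash steps come from the Protocol. The protocol gives no absorbance values, so there is no stated figure to reproduce. The signal sizes below are assumptions, shown as ranges.

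Let C be the net signal of control cells, s the true surviving fraction, b the background in every well, and e the residual extract signal in treated wells only.

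- Treated reading: sC + b + e
- Control reading: C + b
- Apparent cytotoxicity = 1 − (sC + b + e)/(C + b)

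**Step 1: common background only (e = 0).** The expression reduces to (1 − s) × C/(C + b), so true cytotoxicity shrinks by a fixed factor.

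| C | b | C/(C+b) | True 100% reads | True 50% reads |
|---|---|---|---|---|
| 0.8 | 0.05 | 0.941 | 94.1% | 47.1% |
| 0.8 | 0.10 | 0.889 | 88.9% | 44.4% |
| 0.5 | 0.05 | 0.909 | 90.9% | 45.5% |
| 0.5 | 0.10 | 0.833 | 83.3% | 41.7% |

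**Step 2: effect on the ranking.** The factor is the same for every coffee. With C = 0.8 and b = 0.10, true values of 60% and 40% read 60 × 0.889 = 53.3% and 40 × 0.889 = 35.6%. The gap falls from 20 to 17.8 points, but the order and the ratio of 1.5 are unchanged.

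**Step 3: residual extract.** Residue lowers apparent cytotoxicity by a further e/(C + b). With C = 0.8, b = 0.05 and a true 50%:

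- e = 0: 1 − 0.45/0.85 = 47.1%
- e = 0.01: 1 − 0.46/0.85 = 45.9% (1.2 points lower)
- e = 0.02: 1 − 0.47/0.85 = 44.7% (2.4 points lower)
- e = 0.05: 1 − 0.50/0.85 = 41.2% (5.9 points lower)

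Two coffees with the same true effect would differ by these amounts if only one left residue. The error scales with 1/(C + b), so a weaker control signal enlarges it: at C = 0.5 and b = 0.05 the range is 0.01/0.55 = 1.8 to 0.05/0.55 = 9.1 points.

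**Step 4: where residue would matter.** The planned concentrations fall tenfold from 100 to 0.01 µg/ml. If residue is proportional to concentration, e = 0.05 at 100 µg/ml becomes 0.005 at 10 µg/ml, or 0.005/0.85 = 0.6 points, and less below that.

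**Step 5: with blanks.** Subtracting b + e from the treated reading and b from the control reading gives sC/C = s, the true value.

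**The case against.** **Bench detail.** The protocol says absorbance, not uncorrected absorbance, and a laboratory may blank its reader as routine. That is possible. But the document gives an explicit equation and names its only control, so this is more than a detail left to a later analysis plan. If blanking is intended, the protocol should say which wells serve as the blank.

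**Bias in the coffee comparison.** A reader might infer that the missing blank distorts the comparison of green, roasted and decaffeinated coffee. The documents do not support this as an established bias. Common background cannot reorder the coffees (step 2). A coffee-specific error needs extract that survives two PBS washes, replacement by MTT medium and aspiration of that medium. The protocol gives no value for such residue and does not say that the extracts absorb at 570 nm or reduce MTT. The upper figure of about 6 points rests on a residue as large as the whole assumed background; at 0.01 to 0.02 it is about 1 to 2 points. What stands is that the washes reduce residue without measuring it.

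**IC50.** A reader might also infer that reported IC50 values will be too high. Section 10 gives IC50 only as the unit for EGFR on the ELISA reader, and nothing says that one is derived from MTT. If one were, the shift would be modest beside tenfold dilution steps. For a slope-1 curve with C = 1.0, the apparent value is the true one times (1 + b)/(1 − b). An assumed 10 µg/ml would then read 11.1, 12.2 or 15.0 for b = 0.05, 0.10 or 0.20.

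**Importance.** MTT viability is not a primary outcome, so neither primary result is shown to be affected.

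**Conclusion.** The point holds in a limited form. Followed as written, the equation understates cytotoxicity whenever background is above zero. The direction follows from algebra; the size rests on assumed absorbances. For C of 0.5 to 0.8 and b of 0.05 to 0.10, a true 50% reads about 42% to 47%. Differences between coffees shrink by the same factor and keep their order.

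An added coffee-specific error is possible but not shown. It is probably small and largely confined to 100 µg/ml. Because it concerns a supporting measure, this is an inexpensive improvement to make before plates are run, not a flaw that undermines the study.

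**What to change.** On each MTT plate, add cell-free wells without coffee, and cell-free wells with each of the three coffees at least at the highest concentration. Take them through the same incubation, washes, MTT and DMSO steps. Then write:

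% cytotoxicity = 100 × [1 − (treated − matching cell-free blank)/(control − cell-free blank without coffee)]

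Use the no-coffee blank where the extract blank is not plated or does not differ from it.

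The factor of 100 is needed in any case. The present line gives cytotoxicity as a fraction and then subtracts it from 100, so a ratio of 0.60 gives 100 − 0.40 = 99.6% viability instead of 60%.

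**Cost.** The minimum is 3 + 1 = 4 blank conditions. The protocol states no replicate number; assuming triplicates, that is 12 wells beside (3 × 5 + 1) × 3 = 48 test and control wells, or 60 of 96. Blanking every concentration would take 16 × 3 = 48 more and fill the plate, which is why the smaller set is suggested. The reagents are already in use. One limit remains: cell-free wells cannot measure extract retained inside cells.
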